8.1.2. Serious Adverse Event

An SAE is an AE that results in one or more of the following outcomes (International Conference on Harmonization (ICH) E6):

- Death during the period of protocol-defined surveillance.
- Events that are life-threatening (i.e., an immediate threat to life).
- Events requiring hospitalization or prolongation of hospitalization.
- Events resulting in a persistent or significant incapacity or substantial disruption of the ability to conduct normal life functions.
- Congenital abnormalities/birth defects.
- Other important medical events that may jeopardize the subject and may require intervention to prevent one of the outcomes listed above.

All SAEs will be recorded on the *SAE Report Form (F21)*, signed by the PI, and followed until satisfactory resolution, or until the event is deemed chronic or the subject is stable.

Many of the subjects enrolled in this study will have significant influenza-related illness, and it is expected that approximately 40% of enrolled subjects will be hospitalized during their enrollment ED visit due to severe influenza at baseline. If the subject is hospitalized due to their baseline illness, the event will not be reported as an SAE. However if the subject's condition worsens after study drug administration and requires prolongation of the hospitalization, the event will be reported as an SAE. Subsequent events that result in hospitalization after the initial ED enrollment visit will be reported as SAEs (see MOP).

Site PIs will report all deaths and immediately life-threatening events to the IRB within 24 hours of awareness. All remaining SAEs will be reported to the IRB within 7 days of awareness, or per institutional policy.

An ISM will be appointed to provide an independent safety review for SAEs immediately after they occur. The ISM will be a clinician with relevant expertise who is not otherwise associated with the study.

A Safety Monitoring Committee (SMC), consisting of the IND sponsor, JHH Co-PIs, Johns Hopkins University Research Program Manager, BARDA Medical Officer, the ISM, and the study biostatistician will review and monitor the safety and compliance data as well as the overall study progress on a regular basis.

Site PIs will report all SAEs to Westat Regulatory Affairs via fax within one business day of the site's awareness of the event. Westat Regulatory Affairs will notify the ISM and copy the SMC within one business day of the *SAE Report Form (F21)* receipt. The ISM will assess the relationship of the SAE to the study drug and the expectedness of the event to determine the reporting status to the FDA. The ISM will return his assessment to Westat and the SMC within 24 hours. Westat will report the SAE to the FDA per the ISM's recommendation. SAEs will also be reported to BARDA and BioCryst Pharmaceuticals, Inc. (if the subject is in the peramivir arm) within the same timeframe as required by the FDA.

9. Statistical Considerations

9.1. Study Objectives

Primary Objective: To prospectively enroll high-risk subjects with laboratory-confirmed influenza into a randomized, open-label study of oral versus IV influenza therapeutic to include symptom evaluation and outcome assessments.

Secondary Objective 1: To identify influenza-positive patients utilizing a previously established triage-based assessment and rapid testing algorithm for suspected influenza infection.

Secondary Objective 2: To retrospectively evaluate all potentially eligible patients for potential enrollment biases.

Secondary Objective 3: To create a repository of residual NP samples collected from ED patients with suspected influenza illness.

9.2. Sample Size Considerations

The proposed sample size is at least 50 subjects per site, per influenza season. This sample size was determined, in collaboration with ASPR/BARDA, to be adequate for this pilot effort which is being conducted specifically to examine the feasibility of achieving higher recruitment rates than has historically been achieved in other clinical venues, and the ability to reliably collect useful therapeutic endpoint data from an ED enrollment site. Estimates are based on data from the JHH ED 2014-2015 influenza season using the aforementioned testing algorithm, where 1604 patients were tested for influenza between November 2014 and April 2015, and 311 influenza-positive patients were identified. Of those 311 patients, approximately 75% met CDC criteria for influenza treatment (i.e., potential enrollment in the study) and 40% were admitted to the hospital. As 2014-2015 was a robust influenza season, it is estimated that a routine influenza season would have approximately 25% fewer influenza-positive patients. Based on similar previous ED based therapeutic clinical trials conducted at the JHH ED, it is anticipated that 56% of eligible patients will agree to participate in the study. Therefore, assuming a routine influenza season, there will be an estimated 174 eligible patients, of whom 97 will be enrolled (58 discharged, 39 admitted). Based on these estimates, at least 50 (conservatively) and up to 225 subjects could be enrolled and followed for 28 days.

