2.3.1 Outcome Measures and Predictors

Outcomes:

a. For the Primary Objective:

- The number of subjects successfully enrolled
- The proportion of subjects who received treatment with IV study drug in the ED
- The proportion of subjects who received (first dose) oral study drug in the ED
- The proportion of subjects who complete follow-up.

In addition, the following clinical measures will be evaluated for planning future clinical trial endpoints:

- For all study subjects:

- Reported symptoms (including FLU-PRO Symptom Questionnaire)
- Daily functional assessment
- Patient Global Impression of Change (PGIC) on Day 7 and Day 28
- Patient Global Impression of Severity (PGIS) at enrollment, and on Day 7 and Day 28
- Number of subsequent medical visits or hospitalizations within 28 days of enrollment
- Influenza-related complications including pneumonia, myocardial infarction, and stroke.

- For subjects initially admitted to the hospital from the ED:
 - Severity of disease based on Intensive Care Unit (ICU) admission, mechanical ventilation, or oxygen supplementation
 - Ordinal scale up to 14 days:
 - Death
 - Receiving mechanical ventilation or extracorporeal membrane oxygenation (ECMO)
 - In ICU (without mechanical ventilation or ECMO)
 - Non-ICU hospitalization, requiring supplemental oxygen
 - Non-ICU hospitalization, not requiring supplemental oxygen
 - Not hospitalized, but unable to resume normal activities
 - Not hospitalized with full resumption of normal activities.

b. For the Secondary Objective 1:

- The proportion of ED patients who were screened for influenza
- The proportion of screened patients who met testing criteria
- The proportion of patients who met testing criteria who were tested for influenza
- The proportion of patients tested for influenza who were positive for influenza.

c. For the Secondary Objective 2:

- The proportion of eligible patients who were enrolled
- Comparison of demographic characteristics between those who were enrolled in the study versus those who were identified to be potentially eligible through the retrospective chart review.
 - Age
 - Sex
 - Race
 - Ethnicity

d. For the Secondary Objective 3:

- The creation of a robust repository using all remnant samples of patients tested using the triage-based assessment and testing algorithm from November through April 2015 - 2017. Note that this is not a quantitative outcome.

Potential predictors (independent variables) of interest:

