SMC	Safety Monitoring Committee
SOP	Standard Operating Procedure
TAT	Turnaround Time
US	United States

Protocol Summary

Title:	A Pilot Randomized Controlled Trial for Feasibility of Enrolling Subjects for Influenza Therapeutic Trials and Administering Influenza Antivirals in the Emergency Department to High Risk Subjects
Population:	Adults presenting to the emergency department (ED) with laboratory-confirmed influenza who meet Centers for Disease Control and Prevention (CDC) criteria for antiviral treatment
Informed Consent:	Written informed consent
Number of Sites:	2 – large, urban, academically-affiliated, US EDs
Study Duration:	September 2015 – September 2018
Subject Participation Duration:	4 weeks
Description of Agent or Intervention:	Subjects will be randomized to either oral (oseltamivir) or intravenous (IV) (peramivir) antiviral treatment.
Objectives:	
This pilot study is designed to demonstrate the feasibility of utilizing EDs as a primary site for subject enrollment in clinical trials evaluating influenza therapeutics, providing pilot data for future clinical trial design and planning.
 
Primary Objective: To prospectively enroll high-risk subjects with laboratory-confirmed influenza into a randomized, open-label study of oral versus IV influenza therapeutic to include symptom evaluation and outcome assessments.
 
Secondary Objective 1: To identify influenza-positive patients utilizing a previously established triage-based assessment and rapid testing algorithm for suspected influenza infection.
 
Secondary Objective 2: To retrospectively evaluate all potentially eligible patients for potential enrollment biases.
 
Secondary Objective 3: To create a repository of residual nasopharyngeal (NP) samples collected from ED patients with suspected influenza illness.

Description of Study Design:	This is an open-label randomized controlled clinical trial in which subjects with influenza are randomized to either oral (oseltamivir) or IV (peramivir) antiviral treatment.

Estimated Time to Complete Enrollment: Subject enrollment will occur over two influenza seasons (November 2015 – April 2017) or longer, at the co-principal investigators' (Co-PIs') discretion, based on influenza prevalence.

Schematic of Study Design

1. Background

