2.2. Study Outcome Measures

Primary Objective: To prospectively enroll high-risk subjects with laboratory-confirmed influenza into a randomized, open-label study of oral versus IV influenza therapeutic to include symptom evaluation and outcome assessments.

Outcomes: The number of subjects successfully enrolled; the proportion of subjects who complete treatment with IV or oral study drug in the ED; the proportion of subjects who complete follow-up.

In addition, the following clinical measures will be evaluated for planning future clinical trial endpoints:

- For all subjects:
 - Reported symptoms (including FLU-PRO Symptom Questionnaire);
 - Daily functional assessment;
 - Patient Global Impression of Change (PGIC) on Day 7 and Day 28;
 - Patient Global Impression of Severity (PGIS) at enrollment, and on Day 7 and Day 28;
 - Number of subsequent medical visits or hospitalizations within 28 days of enrollment; and
 - Influenza-related complications including pneumonia, myocardial infarction, and stroke.
- For subjects initially admitted to the hospital from the ED:
 - Severity of disease based on Intensive Care Unit (ICU) admission, mechanical ventilation, or oxygen supplementation; and
 - Ordinal scale up to 14 days:
 - Death;
 - Receiving mechanical ventilation or extracorporeal membrane oxygenation (ECMO);
 - In ICU (without mechanical ventilation or ECMO);
 - Non-ICU hospitalization, requiring supplemental oxygen;
 - Non-ICU hospitalization, not requiring supplemental oxygen;
 - Not hospitalized, but unable to resume normal activities; and
 - Not hospitalized with full resumption of normal activities.

Secondary Objective 1: To identify influenza-positive patients utilizing a previously established triage-based assessment and rapid testing algorithm for suspected influenza infection.

Outcomes: The proportion of ED patients who were screened for influenza; the proportion of screened patients who met testing criteria; the proportion of patients who met testing criteria who were tested for influenza; the proportion of patients tested for influenza who were positive for influenza.

Secondary Objective 2: To retrospectively evaluate all potentially eligible patients for potential enrollment biases.

Outcome: The proportion of eligible patients who were enrolled; comparison of demographic characteristics between those who were prospectively enrolled versus not enrolled.

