3.1.3. Run-In Period

Beginning in October and running through April 30 of each influenza season or later, at the co-principal investigators' (Co-PIs') discretion, based on influenza prevalence, all ED patients who are assessed at triage will be evaluated by the CDG and EDSS to determine if they meet the testing criteria of the CDG. To evaluate whether or not the CDG and EDSS are being properly implemented, there will be a run-in period during October of each influenza season. The purpose of this run-in period is to identify and correct any potential problems with implementation of the CDG and EDSS. Principal investigators (PIs) and research staff will closely monitor the implementation of the CDG and EDSS through a standardized monitoring and continuous quality improvement (CQI) process.

During the run-in period, research staff will monitor implementation of the CDG and EDSS to ensure that registered ED patients are screened, and if they meet testing criteria, ensure that the order is placed and the test occurs. Research staff may be on site to act as a resource or to troubleshoot if any problems arise.

Ongoing monitoring will occur throughout the study period (November 1 – April 30 of each influenza season, or later, at the Co-PIs' discretion, based on influenza prevalence). Additionally, the Biomedical Advanced Research and Development Authority (BARDA) personnel will periodically conduct an independent audit to provide relevant feedback which will be informative for guiding future clinical trials.

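### Recruitment rate is a stated purpose of the pilot, but the primary recruitment outcome is a count with no time denominator, tabulated by site and pooled over unequal numbers of seasons

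*Combined protocol and SAP*

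**What the plan says.** **Purpose.** Protocol 9.2, repeated in SAP 2.1, says the size is adequate to examine two things. One is a rate compared with a reference: "feasibility of achieving higher recruitment rates than has historically been achieved in other clinical venues". The other concerns data quality: "the ability to reliably collect useful therapeutic endpoint data from an ED enrollment site".

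**Outcome.** SAP 2.3.1a lists "The number of subjects successfully enrolled" first, followed by the proportions treated in the ED in each arm and the proportion completing follow-up. Protocol 2.2 likewise begins "The number of subjects successfully enrolled; the proportion of subjects who complete treatment with IV or oral study drug in the ED". Neither gives the count a time unit.

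**Target.** Protocol 9.2 opens with "The proposed sample size is at least 50 subjects per site, per influenza season". It is presented as the sample size and is not named as the standard for feasibility.

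**Time.** The Protocol Summary states "Subject enrollment will occur over two influenza seasons", and then allows "or longer, at the co-principal investigators' (Co-PIs') discretion, based on influenza prevalence". Protocol 3.1.3 sets the study period as 1 November to 30 April of each season, "or later, at the Co-PIs' discretion, based on influenza prevalence". Protocol section 4 says that only JHH took part in 2015-2016 and that both sites operate in 2016-2017.

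**Display.** Mock Table 3 has a row for subjects enrolled and columns for site, arm and influenza type. It has no season column. SAP 2.4.6 suggests that the primary outcomes may be compared by site.

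**Reference rate.** No historical figure is given. Protocol 1.1 says only that earlier trials recruited slowly per site and so needed many sites.

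**The concern.** A count answers a rate question only if the time behind it is fixed and shown. Here the sites contribute different numbers of seasons, and each season, as well as the whole enrolment period, can be lengthened. A comparison of the primary outcome by site, which the SAP invites, would then mix speed of recruitment with length of recruitment.

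The pilot exists to help plan later trials. For that purpose the useful number is how many subjects one ED enrols in a month of open screening, because it determines how many sites a later trial needs and for how long. The planned tables do not report it. Nor can a reader judge whether recruitment was higher than elsewhere when no figure for elsewhere is given.

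**Working it through.** **1. The plan's own projection (Protocol 9.2).** Inputs: 311 influenza-positive patients, 25% fewer in a routine season, 75% meeting CDC criteria, 56% agreeing, 40% admitted.

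- Eligible: 311 × 0.75 × 0.75 = 174.9 (plan: 174)
- Enrolled: 174.9 × 0.56 = 98.0 (plan: 97)
- Discharged and admitted: 98.0 × 0.60 = 58.8 and 98.0 × 0.40 = 39.2 (plan: 58 and 39)

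The projection reproduces apart from rounding down. It describes one JHH season and so is itself a figure per site-season.

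**2. Site-seasons.** JHH 2 + MMC 1 = 3. At the target, the total is 3 × 50 = 150.

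**3. What Table 3 would show.** If each site enrols exactly 50 per season:

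| Site | Seasons | Table 3 count | Per site-season | Per site-month (6 months) |
|---|---|---|---|---|
| JHH | 2 | 100 | 50 | 8.3 |
| MMC | 1 | 50 | 50 | 8.3 |

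The rates are equal, yet the counts differ by a factor of two. No extension is needed for this to happen.

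**4. Effect of an extension.** Rate = count ÷ site-months. The extended durations are assumptions for illustration; the documents state none.

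- One site-season of 50: 50/6 = 8.3; 50/7 = 7.1; 50/8 = 6.3 per month. Eight months instead of six lowers the rate by 1 − 6/8 = 25%.
- All three site-seasons, 150 in total: 8.3 over 18 site-months, 7.1 over 21, 6.3 over 24.

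The primary outcome is the same in every case within each line.

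**5. Precision.** The exact Poisson 95% interval for a count x runs from χ²(0.025; 2x)/2 to χ²(0.975; 2x+2)/2.

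- x = 50: 37.1 to 65.9, or 6.2 to 11.0 per month over six months.
- x = 150 over 18 site-months: 127.0 to 176.0, or 7.1 to 9.8 per site-month.

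Influenza arrives in waves, so true variation is probably wider than Poisson. The interval is a description only.

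**6. Whether 56% could serve as a second threshold.** 50/174 = 29%, about half of 56%. A site-season of the projected size could meet the target of 50 and fall far short of 56%. The 56% was also applied to patients meeting CDC criteria, whereas the trial adds a limit of four days of symptoms and twelve exclusion criteria (Protocol 4.2.1), so the denominators differ.

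**The case against.** The case on the other side is substantial. This is a descriptive pilot with no hypothesis tests (SAP 2.4.2), and its primary objective is to enrol and assess subjects. The figure of 50 per site per season is already a benchmark in rate form, so a site-season below 50 visibly misses a figure stated in advance. The count is one of several primary outcomes, and the others address the endpoint-collection half of the purpose. Outcomes are presented by site (SAP 2.3.1), Table 8 shows the share of positives enrolled, and the proportion of eligible patients enrolled is an outcome under Secondary Objective 2. A reader who knows which seasons each site ran can work out an average per season.

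Most of this stands, and it rules out stronger readings. A reader might infer that the trial cannot answer its own question, or that any count could be presented as success. The target of 50 and the other primary outcomes do not support that. A reader might also infer that seasons could be prolonged to reach a number. The documents tie extension to influenza prevalence, and nothing in them suggests another motive.

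What the objection does not remove is the display. Table 3 pools seasons, so whether each site-season reached 50 is not reported, and an average per season hides any extension. Table 8 divides by all test-positives and has no time element. SAP 3.3 leaves the Secondary Objective 2 analysis outside the SAP. It is also fair that monthly enrolment follows influenza activity as well as site performance, and that the first season had already taken place at JHH when this text was written. Both are reasons to keep the comparison with 50 descriptive.

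**Conclusion.** The concern holds in a limited form. Recruitment rate is half of the stated rationale for the sample size. The planned primary recruitment outcome has no time denominator, and its table pools two seasons at one site against one at the other. Followed as written, the table would show a twofold difference between sites recruiting at the same rate, and an extension from six to eight months would conceal a rate 25% lower. The comparison with other venues cannot be made from the documents, because they contain no reference rate.

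The twofold figure rests on the site-seasons set out in Protocol section 4 and on both sites meeting the target exactly. The 25% figure rests on an assumed two-month extension. The sample size, the endpoint-collection outcomes and the descriptive character of the analysis are unaffected. The change is worth making because the missing number is the one that later trials would plan from.

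**What to change.** In SAP 2.3.1a, SAP 3.2 and Table 3:

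1. Add subjects enrolled per site per month of active screening, for each site-season, with a 95% confidence interval (for example exact Poisson). Give the opening and closing dates of screening, and show any enrolment after 30 April separately.
2. Set each site-season's November-April count descriptively beside the plan's own figure of 50 (8.3 per site-month over six months).
3. Show enrolled/eligible alongside, with the denominator defined, and do not use 56% as a pass/fail threshold.
4. Either cite, with its source, the historical per-site rate that the word higher refers to, or limit the conclusion to the observed rate against the plan's own target.

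The cost is SAP wording and some added table columns. Enrolment dates and the Screening and Enrollment Log should supply the data. There are two small downsides: a site-season can visibly miss its target, and monthly rates vary with influenza activity, which a footnote should say. No change to the sample size and no hypothesis test is needed.

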9.3. Final Analysis Plan

As this is an exploratory study, data analysis will be principally descriptive. Rates of discreet events, as well as mean values for numerical data will be calculated. Statistical comparisons between groups (e.g., Secondary Objective 2) will be completed using t-test or chi squared as appropriate. This study is designed to be pilot in nature, and the anticipated sample size (225 subjects) is not sufficient for comparison of outcomes between the two treatment groups. Hence, potential clinical endpoints will be described using descriptive statistics for the purposes of future trial planning, and no statistical comparisons between the oral and PO antiviral arms will be made.

10. Clinical Management Issues

The following clinical management guidelines apply to both treatment groups.

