2.4.2 Hypothesis Testing

There is no hypothesis testing for the study.

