2.4.3 Descriptive Statistics of All Study Variables

Descriptive statistics including mean, median, standard deviation, range for continuous outcomes and frequency/proportion for categorical outcomes will be used to characterize study outcomes.

In addition, we will compare demographic characteristics between those who were enrolled and randomized in the study versus those who were eligible but not enrolled (declined, screen failure, etc.).

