2.4.5 Multiple Comparisons

No adjustment for multiple comparisons will be applied.

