3. STATISTICAL ANALYSIS

3.1 *Analysis of Subject Characteristics*

Subject characteristics will be presented (see Tables 1 and 2). These characteristics will be summarized separately by study arm as well as combined.

3.2 *Analysis of Primary Objectives*

Primary Objective: To prospectively enroll high-risk subjects with laboratory-confirmed influenza into a randomized, open-label study of oral versus IV influenza therapeutic to include symptom evaluation and outcome assessments.

Analysis: Number of patients screened, enrolled and randomized will be plotted in Figure 1. Descriptive statistics including mean, median, standard deviation, range for continuous outcomes and frequency/proportion for categorical outcomes will be used to characterize study outcomes.

All results will be summarized separately by study arm as well as combined. Results will be summarized in Tables 3-7. Ordinal scale up to 14 days for subjects who initially admitted to the hospital from the emergency department, as well as Karnofsky Performance Scale will also be plotted (Figures 2 and 3).

3.3 *Analysis of Secondary Objectives*

Secondary Objective 1: To identify influenza-positive patients utilizing a previously established triage-based assessment and rapid testing algorithm for suspected influenza infection.

Analysis: Frequencies and proportions will be presented in Table 8.

Secondary Objective 2: To retrospectively evaluate all potentially eligible patients for potential enrollment biases.

Analysis: The analysis will involve a retrospective chart review and comparisons of subject characteristics. It is not part of Westat's scope of work, and is therefore not included in this SAP.

Secondary Objective 3: To create a repository of residual nasopharyngeal (NP) samples collected from ED patients with suspected influenza illness.

Analysis: There is no quantitative data collection for this objective. No statistical analysis will be performed.

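### Enrollment bias (Secondary Objective 2): the only stated method is a t-test or chi-squared test, the SAP disclaims testing, and the comparison group is defined inconsistently

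*Combined protocol and SAP*

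**What the plan says.** - **Protocol 9.3** calls the analysis principally descriptive and says that event rates and means will be calculated. It then adds: "Statistical comparisons between groups (e.g., Secondary Objective 2) will be completed using t-test or chi squared as appropriate". It gives no significance level, effect measure or interval for this comparison.
- **SAP 2.4.2**: "There is no hypothesis testing for the study". The sentence is not limited to the treatment arms.
- **SAP 3.3**, on Secondary Objective 2: "It is not part of Westat's scope of work, and is therefore not included in this SAP". The SAP's mock tables contain none for this comparison.
- **SAP 2.3.1(c)** nevertheless lists the comparison as an outcome, on age, sex, race and ethnicity, with the enrolled set "versus those who were identified to be potentially eligible through the retrospective chart review".
- **SAP 2.4.3** lists it again with a different comparator: "we will compare demographic characteristics between those who were enrolled and randomized in the study versus those who were eligible but not enrolled". The list of predictors in SAP 2.3.1 says the same. Both count screen failures among the eligible but not enrolled.
- **Protocol 2.2** compares the prospectively enrolled with the not enrolled. **Protocol 4.1** compares the enrolled with patients not approached and with patients approached but not enrolled. **Protocol 4.1.2** admits to the chart review every adult with a positive influenza test in the season and sets no exclusions.

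**The concern.** The objective asks how far the patients who enrolled differ from those who could have enrolled, so that future trials know whom an emergency department recruits. That is a question of size. A p-value answers a different question and depends heavily on the group counts.

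Three things are unsettled. The protocol prescribes a test, while the SAP says there is none. The SAP repeatedly announces the comparison but names no method and then excludes it, so protocol 9.3 is the only instruction. And the comparator changes from section to section. If SAP 2.3.1(c) is followed as worded, the enrolled sit in both groups. That breaks the independence that t and chi-squared tests assume, and it pulls the visible difference toward zero.

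At stake is a report that gives test results without saying what size of imbalance the data can exclude.

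**Working it through.** **1. Reproduce the plan's counts (protocol 9.2).** Inputs: "311 influenza-positive patients were identified" in 2014-2015; "approximately 75% met CDC criteria for influenza treatment (i.e., potential enrollment in the study) and 40% were admitted to the hospital"; 25% fewer positives in a routine season; 56% consent.
- Eligible: 311 × 0.75 × 0.75 = 174.9 (plan: 174).
- Enrolled: 174 × 0.56 = 97.4 (plan: 97).
- Admitted and discharged: 97 × 0.40 = 38.8 and 97 × 0.60 = 58.2 (plan: 39 and 58).
- Eligible but not enrolled: 174 − 97 = 77.

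**2. Counts at the ends of the plan's range (50 to 225), applying 56% consent.**
- 50 enrolled: 50/0.56 = 89 eligible, 39 not enrolled.
- 225 enrolled: 225/0.56 = 402 eligible, 177 not enrolled.

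**3. Effect of an overlapping comparator.** Let E be the mean or proportion in the enrolled and N that in the not enrolled. The mean over all eligible is (97E + 77N)/174. So E minus the overall mean is (77/174)(E − N) = 0.44(E − N). A true gap of 20 points appears as 20 × 0.44 = 8.9 points. If the overlapping group is instead every influenza-positive adult in a routine season (311 × 0.75 = 233, of whom 233 − 97 = 136 are not enrolled), the factor is 136/233 = 0.58.

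**4. What a test can detect with disjoint groups.** The documents give no alpha, power or base rates for this comparison. I assume two-sided 0.05 and show two base rates.

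Power = Φ[(d − 1.96 × se0)/se1], where d = |p1 − p2|, se0 = √[p̄(1 − p̄)(1/n1 + 1/n2)] with p̄ the pooled proportion, and se1 = √[p1(1 − p1)/n1 + p2(1 − p2)/n2].

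Example, 97 v 77 with 30% v 40%: se0 = 0.0725 and se1 = 0.0727, so (0.10 − 0.1421)/0.0727 = −0.58 and power is 28%.

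| Enrolled v not enrolled | Power, 10 points (50 v 60%; 30 v 40%) | Power, 20 points (50 v 70%; 30 v 50%) | Gap with 80% power, from 50% | Same, standardized |
|---|---|---|---|---|
| 50 v 39 | 15%; 17% | 48%; 48% | 28 points | 0.60 |
| 97 v 77 | 26%; 28% | 77%; 77% | 21 points | 0.43 |
| 225 v 177 | 52%; 55% | 98%; 98% | 14 points | 0.28 |

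The last column is (1.96 + 0.84) × √(1/n1 + 1/n2). With the wider comparator of 136, the 97-subject case has 33% power for 50 v 60% and 87% for 50 v 70%.

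**5. What an interval would show.** The 95% half-width for a trait at 50% is 1.96 × √(0.25/n1 + 0.25/n2). This gives 20.9 points at 50 v 39, 15.0 at 97 v 77 and 9.8 at 225 v 177. The corresponding standardized half-widths are 0.42, 0.30 and 0.20.

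**The case against.** The case on the other side has four parts.

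*Scope.* SAP 3.3 hands Secondary Objective 2 to others, so SAP 2.4.2 can be read as covering only what the SAP contains, with protocol 9.3 governing the rest. This largely stands: the two documents need not be rival methods for one analysis. But 2.4.2 is worded for the whole study, and SAP 2.3.1 and 2.4.3 still list the comparison.

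*Comparator.* SAP 2.3.1 (predictors), SAP 2.4.3, protocol 2.2 and protocol 4.1 all point to patients who were not enrolled. This stands too. The overlap arises from one SAP bullet read literally, and the 44% applies only if that bullet is followed.

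*Decision rule.* A reader might infer that bias will be judged by p-values and that a non-significant result will be reported as no bias. The documents do not say so. They state no alpha and no rule, and protocol 9.3 says that rates and means will be calculated, so the point differences will be available. What is missing is any statement of their precision.

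*Size.* A reader might infer from the 97 v 77 figures that large bias would be missed. Those figures are one routine season projected from one hospital. Protocol 9.3 anticipates 225 subjects, and there a 20-point gap is detected about 98% of the time. The stronger reading fits only near 50 enrolled and, in part, a single routine season. The small counts still have some relevance: the target is at least 50 per site per season, protocol section 4 places the second site in the 2016-2017 season only, and SAP 2.3.1 plans to compare subject characteristics by site for this objective.

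**Conclusion.** The point holds in a limited form. Protocol 9.3 names a test as the only method for Secondary Objective 2, an unqualified SAP sentence says that no testing is done, and one SAP bullet defines a comparator at odds with four other places. The first conflict is partly a scope gap, and the second is a wording error unless the bullet is taken literally.

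The substantive weakness is that a test alone does not measure the bias. At the anticipated 225, large imbalance would be seen, but a 10-point imbalance would be missed nearly half the time. At one routine season it would be missed about three times in four.

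These figures rest on two-sided 0.05, base rates of 30% or 50%, and the plan's 56% consent rate applied at every size. A larger comparator from the full chart review would raise power somewhat.

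**What to change.** 1. In protocol 9.3, for Secondary Objective 2, report the difference in means or proportions with a 95% confidence interval and the standardized difference for each characteristic, in place of the tests or beside them.
2. Name one comparator: enrolled versus eligible but not enrolled, with no patient in both groups. State whether screen failures belong in it, since chart-review entry is wider than trial eligibility.
3. Align SAP 2.3.1(c) with that comparator.
4. Limit SAP 2.4.2 to the treatment-arm comparison, or to the analyses that the SAP contains.

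No numerical cutoff for imbalance or equivalence margin is needed for this; the documents give no basis for a particular value.

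The cost is a few sentences in two documents, with no new data. The downside is that the report may have to say that moderate bias is not excluded for some characteristics, since the intervals will be about ±15 points at 97 v 77 and ±10 at 225 v 177.
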